17.3 Subject confidentiality

The trial staff should ensure that the subject's anonymity is maintained. The subjects will be identified by a subject ID number in the CRF and any electronic database owned by ALK. All documents will be stored securely and only accessible by trial staff and authorised personnel.

17.4 Data protection

All data will be handled and stored according to GDPR (The European parliament 2016).

Investigator

By signing this protocol, the investigator recognises that certain personal identifying information with respect to the investigator and all sub-investigators and trial site personnel, may be used and disclosed for trial management purposes, as part of a regulatory submissions, and as required by law. This information may include:

- Name, address, telephone number and email address
- Hospital or clinic address and telephone number
- Curriculum vitae or other summary of qualifications and credentials
- Financial disclosure information
- Other professional documentation

Consistent with the purposes described above, this information may be transmitted to ALK, affiliates and ALK representative, in the investigator's country and other countries, including countries that do not have laws protecting such information.

Additionally, the investigator's name and business contact information may be included when reporting certain SAEs to regulatory authorities or to other investigators. By signing this protocol, the investigator expressly consents to these uses and disclosures.

In order to facilitate contact between investigators, ALK may share an investigator's name and contact information with other participating investigators upon request.

Subjects

Subjects will be assigned a unique identifier, a subject number. Any subject records or datasets that are transferred to ALK will contain the identifier only; subject names or any information which would make the subject identifiable will not be transferred. This way the subject data will go through a pseudonymisation process, which means that the data cannot be attributed to a specific subject without the use of additional information.

The subject and any biological material obtained from the subject will be identified by subject number, visit number and trial ID. Appropriate measures such as encryption or leaving out certain identifiers will be enforced to protect the identity of subjects as required by local, regional and national requirements.

The subject must be informed that his/her personal trial related data will be used by ALK in accordance with local data protection law. The disclosure of the data must also be explained to the subject.

The subject must be informed that his/her medical records may be examined by auditors or other authorised personnel appointed by ALK, by appropriate IEC members, and by inspectors from regulatory authorities.

Transfer of data

If data are transferred to or accessed by third countries, that is, countries outside EU/EEA countries, the data will be protected to have an adequate level of data protection principles.

Description of arrangements

To ensure the safekeeping of clinical trial data ALK has standard operating procedures that define how data shall be managed including handling of security data breaches. When data is managed by external parties, written agreements are in place to ensure that the data is handled according to ALK's instructions/standards.

17.5 IEC/regulatory authorities

Before initiation of this trial, the protocol, the proposed informed consent form and other information to subjects as well as other documents required, must be reviewed by a properly constituted IEC and provided to the national (and local, if applicable) regulatory authority.

A signed and dated statement that the protocol and the subject information sheet/informed consent form and any other information to the subjects have been approved by the IEC and the regulatory authority must be obtained before trial initiation.

17.6 Inspections

An IEC or a national or international regulatory authority may also wish to conduct an inspection (during the trial or after its completion). If an inspection is requested by a regulatory authority, the investigator must inform ALK of the request immediately. The investigator or ALK should agree (in accordance with the prevailing law) with the inspectors that ALK shall have the right to be present at any inspection or investigation. The investigator or ALK should agree with the inspector that ALK may conduct and control applicable action arising from the inspections at ALK's expense.

The investigator must be available during the inspection and give the inspectors direct and unlimited access to source documentation and data, records and reports used, referenced or created as part of performance of this trial.

17.7 Protocol amendment and other changes in trial conduct

Substantial changes to this protocol require a protocol amendment that must be signed off by ALK and the investigator(s) and be approved by IEC and/or regulatory authorities as applicable before implementation.

The requirements for approval of the substantial changes should in no way prevent any immediate action from being taken by the investigator or by ALK in the interest of preserving the safety of all subjects included in the trial.

Amendments not considered substantial such as administrative changes will only be submitted to the regulatory authorities once another substantial amendment must be submitted or together with the end of trial notification unless national legislation requires otherwise.

18 REPORTING AND PUBLICATION

18.1 Integrated clinical trial report

Data will be reported in an ICTR in compliance with the requirements of the current version of ICH E3: Structure and Content of Clinical Trial Report, ICH GCP Guidelines and ALK SOPs.

The signatory investigator will review and sign the ICTR.

18.2 Publication of results

ALK retains exclusive ownership of all data, results, reports, findings, discoveries and any other information developed or collected during this trial and ALK shall have the exclusive right to use all such information for any purpose, including, but not limited to, use of the results and data either in the form of eCRF (or copies of these), or in the form of a report, with or without comments and with or without analysis, in order to submit them to the regulatory authorities of any country.

By signing the investigator agreement, the investigator agrees that the results of this trial may be used for submission to national and/or international registration and supervising authorities. The authorities will be notified of the investigator's name, address, qualifications and extent of involvement.

It is envisaged that the findings of this trial, including sub-analysis, and if relevant the epidemiology of the screened population and the selection process, will, in due time and by mutual agreement, be published in international journals, theses and/or presented at scientific meetings or symposia. All presentations and publications must be reviewed by ALK prior to public presentation or submission. It is mandatory that the primary publication is based on data from all trial sites, analysed as stipulated in the protocol.

Authorship is based on the International Committee of the Medical Journal Editors "Uniform Requirements" (Vancouver Declaration).

Invitation to author publications will be at the discretion of ALK. All authors of publications need to fulfil all four criteria stated in the Vancouver guidelines/ICMJE (International Committee of Medical Journal Editors) criteria: 1) substantial contribution to the conception or design of the work, or the acquisition, analysis, or interpretation of data for the work; 2) drafting the work or revising it critically for important intellectual content; 3) final approval of the version to be published and 4) agreement to be accountable for all aspects of the work in ensuring that questions related to the accuracy or integrity of any part of the work are appropriately investigated and resolved. Failure to meet all ICMJE criteria will result in removal as author. Other significant contributions to the publication will be acknowledged in accordance with the journal or other relevant specific guidelines.

If the number of authors is restricted, selection will be based on the degree to which individuals can be held accountable for the conduct and reporting of the trial.

Investigators agree not to present data gathered from one trial site or a group of trial sites before the primary publication has been accepted for publication unless formally agreed by all other investigators and ALK.

ALK shall be provided with copies of any proposed publication or presentation at least 60 days in advance of the submission of such proposed publication or presentation to a journal, editor, or other third party. ALK has the right to review and comment on any such publication or presentation within 60 days of receipt but cannot prevent publications of findings. The investigator agrees that all reasonable comments made by ALK will be incorporated into the publication. Furthermore, the investigator agrees that the investigator shall, at ALK's request exclude or delete any confidential information, except trial results generated hereunder, from the proposed publication or presentation.

ALK will review the presentations and publications for accuracy (thus avoiding potential discrepancies with submissions to regulatory authorities), verify that the confidential information is not being inadvertently divulged and/or provide any relevant supplementary information. Upon ALK's request, the investigator shall delay a publication or presentation for 6 months from ALK's receipt of the publication or presentation to permit ALK to file a patent application or take other steps as necessary to protect the confidential information (including trial results of ALK).

Results of the trial will be posted in the EU Clinical Trials Registry (EudraCT) no later than 6 months after the trial is completed (the date of last contact (FU-TC) for the last subject in the trial globally), in accordance with relevant international and national regulations regarding public disclosure of clinical trials. No individual de-identified subject data will be shared.

Results of the trial, together with the final protocol will be posted at ClinicalTrials.gov no later than 12 months after the final completion date (the date of last contact (FU-TC) for the last subject in the trial globally). No individual de-identified subject data will be shared.

19 FINANCE AND INSURANCE

ALK subscribes to an insurance policy covering, in its terms and provisions, ALK's legal liability for injuries caused to participating subjects and arising out of these trial assessments performed strictly in accordance with this protocol as well as with applicable law and professional standards. The compensation to the investigators for work performed under this protocol will be set out in separate clinical trial agreements with the investigators.

20 TRIAL ORGANISATION

The title, name, address and contact details of vendors, including CROs and subcontractors for e.g. project management, monitoring and central laboratory, are listed in Appendix 3.

Appendix 4: Patient paper diary

In order to aid the AE and concomitant medication reporting, subjects will be given a paper diary to fill in daily. The diary will be used by the subject to help remember details and dates, when discussing AEs and concomitant medication with the investigator at the visits.

The diary will be used to capture 15 pre-specified symptoms/signs.

Subjects and their legal representative will be trained by the investigator or designee at V2 on the proper method to complete the diary. The subject will be instructed to report other symptoms, that are not part of the diary solicited list, to the investigator. The reported symptoms will be discussed with the subjects and medically evaluated by investigator and reported as AEs on the AE form in the eCRF, at the discretion of the investigator. The evaluation of the solicited signs/symptoms should be documented in the medical records.

The English master version of the diary can be seen in its full text below.

Protocol: MT-18**Diary for registration of medication intake and symptoms**

Treatment period

Visit 2-3

This section should be completed by the clinic

Start date: ____/____/____ (day/month/year)

Stop date: ____/____/____ (day/month/year)

Welcome to the MT-18 study.

As part of this study, you need to complete this Diary each day with support from your parent/caregiver. You will need to do this from the day you start your study medication and then every day for the next 28 days until you come to the clinic for your final visit.

The purpose of this Diary is to register the following on a daily basis:

- to record if you took your study medication as planned
- to record whether you experience any of the listed symptoms after taking your study medication
- to record if you took any medication to treat any of the listed symptoms

Complete this diary each day and bring the diary to the clinic at your next study visit

		For each day you experienced any of the above listed symptoms, mark whether or not you took any medications to treat these symptoms											
		Yes	No	Yes	No	Yes	No	Yes	No	Yes	No	Yes	No
14) Vomiting													
15) Diarrhoea													
		
Please enter all medications taken today to treat the symptoms you reported above. Please include the symptom (s) treated with this medication. For example "medication x for No 4 " Itching in the mouth"
											

15) Diarrhoea											
For each day you experienced any of the above listed symptoms, mark whether or not you took any medications to treat these symptoms											
	Yes	No	Yes								
Did you take any medication today to treat the symptoms you experienced today?											

Please enter all medications taken today to treat the symptoms you reported above. Please include the symptom (s) treated with this medication. For example "medication x for No 4 "Itching in the mouth"
											

If you experienced other symptoms than the ones listed above, please report the symptoms to the study doctor at the next visit.

For each day you took your study medication, mark whether or not you experienced any of the symptoms listed below:

Page: 9 of 10

For each day you took your study medication, mark whether or not you experienced any of the symptoms listed below:

15) Diarrhoea

For each day you experienced any of the above listed symptoms, mark whether or not you took any medications to treat these symptoms

Please enter all medications taken today to treat the symptoms you reported above. Please include the symptom (s) treated with this medication. For example "medication x for No 4, 'Itching in the mouth'

If you experienced other symptoms than the ones listed above, please report the symptoms to the study doctor at the next visit.

**MT-18 protocol

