6.4 Subject card

All subjects who have signed the informed consent form will be given a subject card by the investigator or qualified designee, identifying them as participants in a clinical trial. The card will contain trial site information (including direct telephone number) to be utilised in the event of an emergency.

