9.3 Treatment of severe allergic reactions/anaphylaxis

If, following exposure to an allergen, multiple organ systems are adversely affected, anaphylaxis is a likely event/diagnosis. Symptoms that may be present during anaphylaxis include flushing, apprehension, syncope, tachycardia, thread or unobtainable pulse associated with a fall in BP, vomiting, diarrhoea and abdominal cramps, wheezing, dyspnoea due to laryngeal spasm, lower airway obstruction, pruritus, rashes (such as urticaria), or angioedema. At V2, the subject and legal representative will be provided verbal and written information, in the form of a local and systemic allergic reaction emergency plan, on how to identify any potential local and systemic allergic reactions including symptoms/signs of anaphylaxis, upper airway obstruction and what actions to take, including phone numbers to call in case of emergency.

In the event of symptoms of anaphylaxis and regardless of use of self-injectable adrenaline/epinephrine, the subject/parent/guardian must immediately call the local emergency number and the 24-hour investigational site emergency number indicated in the informed consent and on the subject identification card. An unscheduled visit will be arranged to further evaluate the subject. The investigator or designee must notify the sponsor within one working day of first becoming aware of the use of self-injectable adrenaline/epinephrine. The symptoms and/or

circumstances that triggered symptoms of anaphylaxis and/or the use of self-injectable adrenaline/epinephrine must be clearly recorded on the eCRF.

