11.16 Solicited signs/symptoms

In order to aid the AE and concomitant medication reporting, subjects will be given a paper diary to fill in daily (See Appendix 4). The diary will be used by the subject to help remember details and dates, when discussing AEs and concomitant medication with the investigator at the telephone contact and at visit 3 (and unscheduled visits, if applicable).

The diary will be used to capture 15 pre-specified symptoms/signs, identified as potential local side effects of sublingual immunotherapy (Passalacqua et al. 2013):

- Food tastes different
- Mouth ulcer/sore in the mouth³⁰

³⁰ A mouth ulcer is a discrete, painful lesion affecting the lining of the mouth where the mucosa is eroded

- Swelling of uvula/back of the mouth
- Itching in the mouth
- Itching in the ear
- Swelling of the lips
- Swelling of the tongue
- Tongue pain
- Tongue ulcer/sore on the tongue³¹
- Throat irritation/tickle
- Throat swelling
- Stomach pain
- Nausea (feel like throwing up)
- Vomiting
- Diarrhoea

If the subject answers “yes” to any of the symptoms, listed in the diary, the subject must also fill in whether any medication was used to treat this symptom and what type of medication.

Subjects and their legal representative will be trained by the investigator or designee at V2 on the proper method to complete the diary. In addition, the subject will be instructed to report other symptoms, that are not part of the diary list, to the investigator. The reported symptoms will be discussed with the subjects and after medical evaluation by the investigator be reported as AEs on the AE form in the eCRF. The evaluation of the solicited signs/symptoms must be documented in the medical records.

When evaluating the diary together with the subject at V3 the investigator should identify use of medication reported on the diary and fill each use of medication into the eCRF linked to the relevant AE.

If any AEs are reported on several consecutive days, the investigator should mark the AE as “recurrent” and inquire about the approximate duration each day of these recurring AEs and enter this information into the eCRF (see section 12.3).

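### The readable diary text sends every unlisted symptom to the next visit; one reworded sentence would bring it into line with the emergency instructions in section 9.3

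*Combined protocol and SAP*

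**What the plan says.** The diary in Appendix 4 is a paper form completed daily at home with parent or caregiver support. It lists 15 symptoms. For anything else it says: "If you experienced other symptoms than the ones listed above, please report the symptoms to the study doctor at the next visit". The sentence appears twice in the readable text, with no exception and no mention of the emergency plan.

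Two other places give the same instruction without a time. The Appendix 4 introduction says: "The subject will be instructed to report other symptoms, that are not part of the diary solicited list, to the investigator". Section 11.16 says: "the subject will be instructed to report other symptoms, that are not part of the diary list, to the investigator".

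Section 9.3 sets the urgent route. With symptoms of anaphylaxis, "the subject/parent/guardian must immediately call the local emergency number and the 24-hour investigational site emergency number". Among the possible signs it names are "wheezing, dyspnoea due to laryngeal spasm, lower airway obstruction, pruritus, rashes (such as urticaria), or angioedema". At V2 the subject and legal representative receive verbal and written information "on how to identify any potential local and systemic allergic reactions including symptoms/signs of anaphylaxis, upper airway obstruction and what actions to take". Section 6.4 adds a subject card: "The card will contain trial site information (including direct telephone number) to be utilised in the event of an emergency".

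**The concern.** The diary is the form the subject handles every day, and it is the only place that attaches a delay to unlisted symptoms. Read literally, it asks an adolescent with hives or a brief wheeze after a home dose to mention it at the next visit.

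Only the first dose is supervised (section 8.1), and section 1.4 notes that some serious systemic reactions have followed later doses. The Table of definitions treats systemic allergic reactions as graded, with anaphylaxis as the severe end. Section 12.1.1 makes them events of special interest. The 24-hour report to the sponsor under section 12.3.3 runs from the investigator's knowledge of the event. If a milder reaction is held back for the next visit, the investigator learns of it late and daily dosing continues meanwhile.

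**Working it through.** The plan gives no figure of its own on this point. The check compares two symptom lists and then counts days.

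**Which section 9.3 signs fall outside the diary list**

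- Section 9.3 names 14 signs: flushing, apprehension, syncope, tachycardia, weak or absent pulse with falling blood pressure, vomiting, diarrhoea, abdominal cramps, wheezing, dyspnoea, lower airway obstruction, pruritus, rashes and angioedema.
- Three are diary items: vomiting, diarrhoea and stomach pain.
- Two are partly covered: pruritus (mouth, ear) and angioedema (lips, tongue, uvula, throat).
- Not covered: 14 − 3 − 2 = 9.

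The nine should not be read as nine things a subject would defer. Tachycardia, pulse with blood pressure, and lower airway obstruction are largely for a clinician to assess. The ones a subject would plainly notice are flushing, fainting, wheeze, breathlessness and rash or hives.

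**What the next visit means**

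The diary cover reads Visit 2-3, and the form is to be brought to the clinic, so V3 is the natural reading. The telephone contact in between is nevertheless a real opportunity. Table 2 has the site assess AEs on that call, section 12.3 requires the question at every contact, and section 11.16 has the diary used "when discussing AEs and concomitant medication with the investigator at the telephone contact and at visit 3".

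**Delay if the subject relies on the diary alone**

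Inputs from the flow chart: telephone contact on Day 8 ± 1, so Day 7 to 9; V3 on Day 29 + 3, so Day 29 to 32; doses on Days 1 to 28, assumed uninterrupted.

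*Onset on day d, after the call:* the delay to V3 is (29 − d) to (32 − d) days, with 28 − d further doses. For d = 14:

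- 29 − 14 = 15 to 32 − 14 = 18 days
- 28 − 14 = 14 further doses

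*Onset on day d, before the call:* the delay to the call is (7 − d) to (9 − d) days. For d = 2:

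- 7 − 2 = 5 to 9 − 2 = 7 days
- 5 to 7 further doses, counting the dose on the day of the call

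Section 3.1 places the call 7-9 days after V2, which is Day 8 to 10. On that timing the Day 2 case becomes 8 − 2 = 6 to 10 − 2 = 8 days.

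An unscheduled visit, which section 3.1 allows for safety follow-up, would shorten any of these.

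**The case against.** The strongest reply is that there is no contradiction. The diary is a recording tool, its sentence concerns telling the study doctor, and it nowhere says to wait before seeking help. A subject can follow both instructions. This stands. A reader might infer that the diary overrides section 9.3, or that the trial lacks a safeguard for anaphylaxis. The documents do not support that: the written plan, the V2 instruction to both subject and legal representative, and the telephone numbers on the card and in the consent form all address it.

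A related reply is that the section 9.3 rule is triggered by symptoms of anaphylaxis, introduced where several organ systems are affected, whereas the realistic harm is a milder reaction. This also stands in part. Milder reactions belong to the local and systemic allergic reaction emergency plan. Its text is not in the documents, so how it handles them cannot be checked. The point therefore rests more on the delay that only the diary sentence adds than on a breach of section 9.3.

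A reader might also take the Day 2 case through to V3, giving 29 − 2 = 27 to 32 − 2 = 30 days and 26 further doses. That requires the telephone contact to miss the event, although the site must ask about AEs on that call. The figure should not be used.

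Timing also favours the plan. Section 3.2 says IMP-related AEs generally begin in the first few days, with few new ones after the first weeks, so a Day 14 onset is less typical than one that the call would catch.

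Finally, the diary has 10 pages and its grid pages are only partly readable. The welcome and purpose text is readable and has no pointer to the plan, but one elsewhere cannot be ruled out.

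**Conclusion.** This is a cheap improvement to one patient-facing sentence. In its readable text the diary adds a delay that section 11.16 and the Appendix 4 introduction do not ask for, and that sits poorly with the immediate-call rule.

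The exposure is a milder or ambiguous systemic reaction at home, in a subject who relies on the diary alone. On that assumption the delay is about 5 to 7 days for a Day 2 onset, and 15 to 18 days with 14 further doses for a Day 14 onset.

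The documents do not say how often a subject would follow the diary in preference to the plan, so no expected number of events can be given. The baseline risk is low: section 1.4 describes few serious post-marketing cases, and section 15.1 reports no severe systemic reactions in 265 adolescents on 12 SQ-HDM. No endpoint analysis changes.

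**What to change.** Replace the sentence, wherever it appears in the diary, with:

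> If you have trouble breathing, wheezing, widespread rash or hives, flushing, fainting or serious swelling, follow your allergic reaction emergency plan immediately and do not wait for a visit. Report any other unlisted symptoms to the study doctor at the next contact (telephone call or visit).

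This points to material the subject already holds and counts the telephone contact as a reporting occasion. It should not be widened to require calls for mild local symptoms, which section 1.2 describes as frequent and transient.

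The cost is rewording and re-translating one paper form, ethics committee review of the revised form (section 17.5 covers information to subjects), and a few more calls to sites. If the complete diary already carries an equivalent pointer, the sponsor need only confirm it and change the timing to the next contact.

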9.4 Temporary interruption of treatment

Treatment may be interrupted for up to 7 days due to any of the following reasons:

- In case of oral surgery, including dental extraction and shedding of a tooth, to allow healing of the oral cavity
- Inflammatory conditions in the oral cavity
- Upper airway viral infection in an asthmatic subject
- Other reasons if deemed necessary by the investigator

Interruptions should be kept to a minimum. If IMP is interrupted for more than 7 consecutive days, the subject should be discontinued.

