12.3.1 Solicited AEs

The diary (See Appendix 4) will be used by the subject to help remember details and dates, when discussing AEs and concomitant medication with the investigator at the visits.

The diary lists 15 specific signs/symptoms, identified as local side effects of sublingual immunotherapy (Passalacqua et al. 2013). These local side effects will be collected on a daily basis by the subject during the 28 days of treatment (section 11.16).

See Appendix 5 for preferred terms used (PT) to identify solicited AEs.

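### The diary's symptom prompt is tied to days on which study medication was taken, contradicting the daily 28-day collection stated elsewhere, so listed symptoms on off-dose days get no daily prompt

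*Combined protocol and SAP*

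**What the plan says.** The protocol body describes daily collection without any condition on dosing. Section 11.16 states that "subjects will be given a paper diary to fill in daily", and section 12.3.1 says that the 15 listed local effects will be "collected on a daily basis by the subject during the 28 days of treatment". The introduction to the diary in Appendix 4 agrees. It tells the subject: "You will need to do this from the day you start your study medication and then every day for the next 28 days", and later: "Complete this diary each day and bring the diary to the clinic at your next study visit".

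Two other instructions in the same diary are narrower. One of its stated purposes is "to record whether you experience any of the listed symptoms after taking your study medication". The header over the symptom grid, which is visible twice, reads: "For each day you took your study medication, mark whether or not you experienced any of the symptoms listed below".

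Section 9.4 expects that some subjects will have off-dose days. It allows treatment to be paused for up to 7 days and calls for discontinuation only when more than 7 consecutive days are missed. One of its four listed reasons is "Inflammatory conditions in the oral cavity". Another is oral surgery or loss of a tooth. The remaining two are upper airway viral infection in a subject with asthma and other reasons judged necessary by the investigator.

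**The concern.** A subject who follows the grid header to the letter leaves the symptom rows empty on any day without a tablet. The diary is the trial's tool for active solicitation, and having one or more solicited TEAEs is a secondary endpoint (section 2.3). Section 15.8.1 also summarises numbers of events, and duration and time to onset for the most frequent AEs. The diary is meant to help subjects remember the dates behind those summaries.

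The gap need not fall on neutral days. The list includes mouth and tongue ulcers, tongue pain and swellings. If an oral condition leads to a pause, the prompt drops out when such symptoms are plausible.

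**Working it through.** **1. The plan's own figure.** The documents give no interruption rate, missed-dose rate or expected diary completeness, so there is no figure on this point to reproduce. The only computed design figure is in section 15.1: an upper limit of 0.95% for the two-sided 90% interval with 1 event in about 500 adolescents. The exact (Clopper-Pearson) limit is the 0.95 quantile of Beta(x+1, n−x). With x = 1 and n = 500 it is 0.945%, so the figure reproduces. The diary wording does not affect it.

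**2. The instructions side by side.**

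| Place | Days covered |
|---|---|
| Section 11.16 | every day |
| Section 12.3.1 | every day of the 28-day treatment period |
| Appendix 4, introduction | every day, no condition on intake |
| Appendix 4, purpose statement on symptoms | symptoms following intake |
| Appendix 4, grid header | days with intake only |

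**3. Which symptoms are left without a diary instruction.**

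- Listed symptom, dosing day: covered by the grid.
- Unlisted symptom, any day: covered by the note under the grid to tell the study doctor at the next visit.
- Listed symptom, off-dose day: covered by neither, if the header is taken literally.

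**4. Share of days affected.**

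- One missed dose: 1/28 = 3.6%.
- One interruption of the longest permitted run: 7/28 = 25%.
- Total over the period: section 9.4 limits consecutive days, and no limit on the sum is stated. The arithmetical extreme starts with a dose on Day 1 and separates runs of 7 by single dosing days: 1+7+1+7+1+7+1+3 = 28. That is 4 dosing days and 7+7+7+3 = 24 off-dose days. It is not a realistic case, since section 9.4 asks that interruptions be kept to a minimum, but it shows that 7 is a limit per run.

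**5. What can reach the secondary endpoint.** A subject's status changes only if three things hold together. Let f be the proportion of subjects with any off-dose day, u the proportion of those whose only listed symptoms fall on off-dose days, and m the proportion of those whose symptom is also missed by questioning. The understatement of the endpoint proportion is then f × u × m, which cannot exceed f. None of the three is given, so no value can be calculated. Section 3.2 says that IMP-related AEs generally appear within the first few days of treatment. That suggests a small u, because most affected subjects would already have a listed symptom on a dosing day.

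**The case against.** The strongest reply is that the diary is a memory aid and not the AE record. Under section 12.3, subjects are asked about problems at every contact, and each AE has one form from start to resolution. Section 12.3.4 requires non-serious AEs to be followed to resolution or the follow-up call. Section 11 has the investigator ask the subject about unclear diary entries. Subjects are trained at visit 2 and can be re-instructed at the Day 8 call. Appendix 5 classes any AE with a listed preferred term in the 28 days as solicited, with no diary tick needed. Many subjects will also follow the introduction and fill in every day. All of this stands, and it limits the harm to the loss of a daily prompt. It does not make the instructions consistent, and open recall at the Day 8 call and visit 3 is the less active method that the diary is meant to support. Appendix 5 is also not the only definition: the Table of definitions ties a solicited AE to what the diary reports, so an off-dose symptom found only by questioning could be classed differently under the two.

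It can also be said that intake-linked wording reflects the design, because section 12.3 closes a recurrent AE once it no longer follows intake. That rule sets a stop date. It does not restrict the days on which symptoms are solicited.

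A reader might infer that pauses are often caused by oral reactions, so that the missing days are informative. The documents do not support this: two of four listed reasons are oral, one of those is surgery or tooth loss, and no frequencies are given. A reader might also infer that AE durations are cut short by up to 7 days. That does not follow either, because durations come from the dates on the AE form and not from counts of diary ticks.

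Finally, the grid pages are incomplete in the text available for this review. An instruction for missed-dose days elsewhere on the grid cannot be excluded.

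**Conclusion.** The point holds as a minor inconsistency in an operative data-collection instruction. The grid header and one purpose statement make the symptom prompt depend on intake, while sections 11.16 and 12.3.1 and the diary's introduction do not. Taken literally, listed symptoms on off-dose days lose their daily prompt: 25% of diary days for one maximal interruption, less for isolated missed doses, and possibly more if interruptions recur. The consequence is possibly weaker recall of onset and stop dates on those days. Any effect on the proportion with a solicited TEAE would be downward and is probably small, but its size is unknown. This rests on subjects following the header literally and on there being no overriding instruction in the parts of the grid that cannot be seen.

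**What to change.** Reword the grid header so that it asks about every day of the period regardless of intake, for example: *On every day, including days without a tablet, tick whether you had any of these symptoms.* Align the purpose statement in the introduction by removing the link to intake. Keep tablet intake as its own daily entry, which the diary already provides for, so that symptoms can still be related to dosing in the analysis. It would also help to bring the solicited-AE entry in the Table of definitions into line with Appendix 5.

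The diary change costs revised text and translations only. No visit, dose, interruption rule or analysis changes.
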